6. EXTENSION TRIAL

Background and Preliminary Results

As stated in our initial study protocol, patients demonstrating a year-1 increase in height SDS $> + 0.3$ will qualify to enroll in the extension trial, which will allow continuation of GH therapy for another two years, while using the same GH dosing protocol as for year 1. Of the five patients receiving GH therapy for at least six months, results from their 6-month study visits yield a favorable growth response. The annualized mean height velocity for this group is 9.4 cm/yr (range, 7.4 to 11.2 cm/yr). The annualized mean increase in height SDS is $+ 0.8$ (range, $+ 0.5$ to $+ 1.4$). Even the lowest responder achieved a gain in height SDS of $> +0.3$ (namely, $+ 0.5$ SDS), and thus qualifying for further treatment with GH as part of the study's extension trial requirements. All families have shown good practice adherence with both the GH injections, and the follow-up study visits so far. At this point, GH therapy is not FDA-approved for ACAN deficiency associated growth failure. There are, to our knowledge, no other trials for this disorder available to the patients with ACAN deficiency.

Specific Objective for the extension trial

Primary objective:

- Describe the continued effects (beyond year 1) of GH therapy on growth parameters in pre-pubertal children with ACAN deficiency.

Secondary objective:

- Continue to describe features of joint involvement, as noted on physical exam or history, in patients with ACAN deficiency receiving continued GH treatment - to provide additional insights into the underlying joint pathophysiology present in ACAN deficiency.

Study Design and Methods

Study Hypotheses:

1. Continued treatment with GH in children with ACAN deficiency will result in ongoing catch-up growth due to increased growth velocity.
2. Early joint pathology demonstrated on prior MRI will be evident on clinical examination of affected subjects.

Endpoints:

- A. Primary Outcome – Change in height SDS from 12 to 36 months, and overall delta height SDS from start of therapy to 36 months.
- B. Secondary Outcomes
 - a. Height velocity in cm/year calculated for each year of the trial.
 - b. Change in height velocity during years 2 and 3 of GH therapy.
 - c. Change in bone age divided by change in chronological age for each year of continued therapy.
 - d. Change in whole body bone mineral density adjusted for height at 24 and 36 months.
 - e. Frequency of adverse events as defined below.
 - f. Frequency of joint complaints.

Study Recruitment

Only study participants that have had a satisfactory response to GH within the first year of treatment will have the opportunity to enroll in the extension trial. This is defined as an increase of height SDS of + 0.3 or greater.

Study protocol

This is an extension trial of rhGH therapy in pre-pubertal children with ACAN deficiency. The primary outcome measures of interest are height velocity and change in height SDS. All patients currently in the treatment trial will continue to receive once daily injections of Norditropin at a standard dose of 50 mcg/kg/day, per initial study protocol (this dose can only be adjusted based on safety guidelines as described in the original protocol for year 1 of therapy, i.e., if IGF-I concentration on therapy is $> +2.5$ SD)

Follow up visits will occur every 6 months, or semi-annually. Study staff will continue to perform check-in calls every 3 months to promote compliance and to record any missed doses, potential new adverse events or use of concomitant medications. In addition, study staff will dispense an additional 3 months of medication and supplies after the 3-month check confirms adequate adherence with the study protocol and no new treatment-related adverse events were reported. Each follow-up visit has a +/-2-week window to accommodate participant schedules and travel. These visits will be the same as previous ones performed for the initial 12-month trial.

The chart below outlines the visit activity schedule **for the extension trial**.

Lab/Assessment	Check-in Calls	18- and 30-Month Visits	24- and 36-Month Visits
Physical exam		X	X
Vital signs		X	X
Height/weight		X	X
TSH		X	X

Free T4		X	X
IGF-I		X	X
IGFBP-3		X	X
Bone Age X-ray			X
DXA scan (whole body, lumbar spine) *			X
Compliance Review	X		
Adverse Event Review	X		
Medication Dispensation	X	X	X

*Additional radiation will be received, approx. 0.013mSv per scan

Only if a participant was unable to complete a study procedure during the initial 12-month trial period due to age, scheduling conflicts, or illness, they may be asked to perform the procedure during the extension trial at one of their scheduled study visits (i.e., MRI, gait assessment, musculoskeletal evaluation).

After each study visit, we will send a letter summarizing the exam findings and lab results to the participant's local primary care physician or pediatric endocrinologist.

Reasons for Completion of the Clinical Trial Participation

When it becomes clear that a participant is no longer benefitting from ongoing GH therapy, treatment will stop.

To discontinue further GH therapy during the extension trial, either of the following must occur:

1. The participant reaches skeletal maturity according to their most recent bone age x-ray.
2. The participant has a height velocity of <2.5 cm/yr.
3. The participant and/or his/her family feels continued therapy does not lead to satisfactory treatment response.
4. The participant has completed their last study visit (3 year) and there is no more funding to continue the trial.

The treatment portion of the trial will be discontinued for an individual subject if he or she develops a serious adverse drug reaction (as defined below). The treatment trial may otherwise be discontinued if the subject withdraws consent or if the PI determines that the subject is no longer eligible to continue treatment. Participants that discontinue the treatment portion of the trial will be encouraged to follow up with their local pediatric endocrinologist for follow-up care and management.

If a subject's participation (and treatment) ends due to 1) completion of the trial and/or 2) lack of continued funding, study staff will work with the family to establish clinical care and GH treatment through a local pediatric endocrinologist. Up to 3 months' worth of medication and supplies can be dispensed to the family at the last study visit to ensure continuity of ongoing care during this transition period.

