5. RESEARCH DESIGN AND METHODS

Study Hypotheses:

1. Treatment with GH therapy will increase growth velocity in children with ACAN deficiency.
2. Early joint pathology will be evident on MRI examination of affected subject's knees and will provide insights into the underlying joint pathophysiology present in ACAN deficiency.

Endpoints:

- A. Primary Outcome – Change in height SDS from baseline to 12 months.
- B. Secondary Outcomes
 - a. Height velocity in cm/year calculated over 12 months of trial.
 - b. Change in height velocity. Baseline height velocity will be based on review of the medical records using the documented height closest to 12 months prior to the screening visit.
 - c. Change in bone age divided by change in chronological age.
 - d. Change in whole body bone mineral density adjusted for height.
 - e. Frequency of adverse events as defined below
 - f. Frequency of joint complaints using measures described below.
 - g. Frequency of cartilage disease based on MRI evaluation of the knee as described below.

Study type

This is an open-label single arm prospective study examining the effects of a single dosing regimen of daily GH on growth response over a 12 month –followed by a four-year extension period in children with ACAN deficiency. The projected dose of GH that will be used is 50 micrograms/kg/day. This dose was initially chosen as it is within the approved range for Norditropin® for non-GH deficient states, including Turner Syndrome and Noonan Syndrome. Additionally, a parallel phenotyping study was done in affected first degree relatives of the subject.

We have elected not to have a control arm for two reasons. First, our preliminary retrospective data suggests that GH does increase HV in patients with ACAN deficiency. Additionally, the retrospective data show that patient's height SDS score will decline over time without intervention. Thus, patients and their families are highly motivated to pursue GH therapy and are unlikely to consent to be part of a study which includes a control arm. Near one-hundred percent compliance (limited missed daily GH injections) and persistence with the protocol has been observed in our cohort so far for patients at least one year on therapy and as long as 30 months. Second, this is a rare disorder, and we did not think it is feasible to recruit sufficient numbers of patients in a reasonable time frame to conduct an adequately powered randomized controlled trial.

.

Study population

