 - G. Note – ADHD treated with a stimulant and treated hypothyroidism with a normal TSH will NOT exclude the subject from participating in the trial.
5. Malnutrition – Defined as a BMI <5th percentile (CDC growth charts)
6. Any clinically significant abnormality on screening laboratory tests as determined by the principal investigator.
7. Known or suspected allergy to trial medication, excipients, or related products.
8. Contraindications to study medications, worded specifically as stated in the product's prescribing information.
9. The receipt of any investigational drug within 90 days prior to this trial.

Withdrawal Criteria

The subject may withdraw at will at any time. The subject will be withdrawn if she becomes pregnant or intends to become pregnant. This should not be an issue as all subjects are pre-pubertal at onset of the trial.

Subject Replacement

If a subject is withdrawn from the study at any point, an additional subject will be recruited to meet our goal of 10 subjects completing 1 year of the study.

Rationale for Study Population

If a subject is withdrawn from the study at any point, an additional subject will be recruited to meet our goal of 10 subjects completing one year of the study. This has been reached. Any future drop out from the study will not be replaced by new recruitment as all 10 subjects are past the one-year treatment mark.

Subject Recruitment/Consent

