- B. GH initiation – If the subject passes screening, a supply of GH therapy will be shipped to the subject from the study coordinator. The supply amount will be determined by what is needed for the 3 months +/- 2-week window until the next check-in/visit to ensure that subjects do not run out of medication. Receipt of GH will be confirmed via telephone call and the date of GH initiation will be recorded. A log will be provided to the subject to record daily compliance for the first year of treatment with GH.
- C. 1-week telephone call – A telephone call will be made at 1 week (+/- 2 days) to review GH administration and address any issues with medication administration.
- D. 3-month telephone call and remote lab draw – A telephone call will be made at 3 months (+/- 2 weeks) to review compliance and assess for any adverse events that may not have been previously reported (See Adverse Event reporting section). After successful completion of this call, an additional 3 month +/- 2-

week supply of GH will be shipped to the subject. A lab slip will be provided for measurement of IGF-1 level at a local lab. This value is only being used as a safety measure and not as an efficacy outcome measure and thus will not be centralized. It will logically not be possible to centralize this sample.

E. 6-month visit – The subject will return to CCHMC 6 months (+/- 2 weeks) after initiation of GH therapy for a repeat visit. The subject will undergo a routine physical examination including a focused joint exam (inspection of the hip joints, checking for scoliosis) and pubertal staging performed by a pediatric endocrinologist. Vital signs will be obtained. Weight will be measured on a digital scale. Height will be measured in triplicate on a standing stadiometer which is calibrated daily. The average of the three measurements will be used. A funduscopic exam will be performed. Labs will be performed as detailed in **Table 1**. The compliance log will be reviewed, and the subject will be assessed for any adverse events that may not have been previously reported. The dose of GH will be weight adjusted to maintain a dose of 50 micrograms/kg/day. An additional 3 month +/- 2-week supply of GH will be provided to the subject.

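### Does treating an annualised six-month gain of +0.5 SDS as already qualifying, with the +0.3 cut-off worded two ways, leave entry to the extension unclear?

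*Combined protocol and SAP*

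**What the plan says.** Section 6, Background and Preliminary Results, states that "patients demonstrating a year-1 increase in height SDS" above +0.3 may enter the extension. It then reports five patients, using their six-month visits: "The annualized mean increase in height SDS is" +0.8, with a range of +0.5 to +1.4. The next statement reads "Even the lowest responder achieved a gain in height SDS of" more than +0.3, gives the value as +0.5, and describes the child as "thus qualifying for further treatment with GH as part of the" extension.

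Section 6, Study Recruitment, restates the rule as a satisfactory response within the first year of treatment: "This is defined as an increase of height SDS of + 0.3 or greater".

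Three places in Section 5 bear on this:
- Endpoints defines the year-1 primary outcome as the change in height SDS from baseline to 12 months.
- Growth Hormone Trial Procedures gives the timing of the six-month visit: "The subject will return to CCHMC 6 months (+/- 2 weeks) after initiation of GH therapy". Baseline height is measured at screening, before drug is shipped.
- Rationale for Study Population says "all 10 subjects are past the one-year treatment mark" and that later dropouts will not be replaced. Study type likewise refers to "patients at least one year on therapy and as long as 30 months".

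**The concern.** A first-year gain cannot be known at month 6. The preliminary-results paragraph sets a 12-month criterion, reports annualised six-month data, and then treats the lowest annualised value as a gain already made that satisfies the criterion. Read literally, the protocol's only worked example applies the rule to a projection.

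The second difficulty is the cut-off. One subsection asks for more than +0.3 and the other accepts +0.3 itself, so a child recorded at exactly +0.3 is out under one and in under the other.

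The rule decides who may continue growth hormone and who contributes to the extension's primary outcome from 12 to 36 months. If its measurement basis or boundary were truly uncertain, membership of the extension cohort could depend on which sentence was followed.

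**Working it through.** **Where +0.5 comes from.** It equals the minimum of the annualised range given one sentence earlier (+0.5 to +1.4), so it is the annualised figure. The raw six-month gain is not reported.

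**Observed gain, if annualisation was linear (assumption).** Observed gain = annualised gain × days between heights ÷ 365.25. Six months is 182.6 days, and the visit window of 14 days either side gives 168.6 to 196.6 days.

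| Annualised value | 168.6 days | 182.6 days | 196.6 days |
|---|---|---|---|
| 0.45 (lower rounding limit) | 0.208 | 0.225 | 0.242 |
| 0.50 | 0.231 | 0.250 | 0.269 |
| 0.55 (upper rounding limit) | 0.254 | 0.275 | 0.296 |

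On these inputs every value is below +0.3.

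**Why that does not settle the matter.** The table counts days from the first dose, while baseline height is taken earlier, at screening. If annualisation used the interval between the two heights, the screening-to-start lag adds to each column. That lag is not stated. The interval at which the observed gain equals 0.3 is 0.3 ÷ annualised value × 365.25:
- For 0.55: 0.3 ÷ 0.55 × 365.25 = 199.2 days. The lag needed is 199.2 − 196.6 = 2.6 days at the late edge of the window, or 199.2 − 182.6 = 16.6 days at a nominal six months.
- For 0.50: 0.3 ÷ 0.50 × 365.25 = 219.2 days. The lag needed at a nominal six months is 219.2 − 182.6 = 36.6 days.

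A short lag could therefore put the observed gain at +0.3. About +0.25 is a plausible central value, but a gain below +0.3 is not established.

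**What the child still needed.** At the central value, 0.3 − 0.25 = 0.05 over the second half-year. That is 0.05 ÷ 0.25 = 20% of the first half-year's gain. At the lower rounding limit and a nominal six months it is 0.3 − 0.225 = 0.075, or 0.075 ÷ 0.225 = 33%. Reaching +0.3 by month 12 required only a fraction of the pace already seen.

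**Strict versus inclusive cut-off.** The two differ only for a gain recorded as exactly +0.3. Section 11 gives planning values of mean 0.407 and SD 0.343. Assuming normality, the chance that a child is recorded at +0.3 is:
- unrounded: nil;
- two decimals: P(0.295 ≤ X < 0.305) = 0.011;
- one decimal: P(0.25 ≤ X < 0.35) = 0.110.

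The recording precision is not stated, so the 11% rests on an assumed one-decimal decision rule. The planning values are also retrospective. Section 3 says those children had differing regimens, some with a GnRH analog or aromatase inhibitor as well. The trial's own early figures (annualised mean +0.8, lowest +0.5) lie further from +0.3, so 11% is more likely too high than too low.

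**The case for a change.** The strongest case for acting is that the core point needs no assumption: whatever the raw value was, a six-month projection cannot satisfy a year-1 criterion. The sentence that declares the child qualified drops the annualised label. The paragraph is also stale, since observed 12-month gains should exist for all 10 children. An entry rule should have one wording and one basis, and the repair costs a few sentences.

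Much of this stands. The wording is loose, the data are superseded, and the two cut-off sentences contradict each other at the boundary.

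What does not stand is that the reader is left unsure of the basis for entry. Both statements of the rule refer to the first year, and the matching endpoint runs from baseline to 12 months. One illustrative sentence in a background paragraph does not amend that. The same paragraph also says that the data come from six-month visits and are annualised, so nothing is concealed. An analyst or coordinator applying the rule would use the 12-month height, and the protocol schedules that measurement for every child.

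**Conclusion.** No change to the plan follows. An annualised six-month figure is described as a gain already achieved, and the cut-off has a clerical mismatch between its strict and inclusive forms. Neither alters the design, the endpoint definitions, the analysis or a conclusion. The year-1 primary outcome does not depend on the +0.3 rule, and Section 11 describes all outcomes as descriptive with no formal comparison. All 10 children have passed one year and none will be replaced, so no first-year gain remains to be projected.

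The size is small. The illustrative child was about +0.05 SDS short of the cut-off at six months on the central reading, and may not have been short at all. The two cut-offs differ only at exactly +0.3. The central reading assumes linear annualisation and ignores the unknown screening-to-start lag. The documents show no child wrongly enrolled or excluded.

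The two statements of the cut-off in Section 6 must still be reconciled as a matter of wording. Which form applies, and to what precision a gain is recorded, are for the sponsor to state.

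### Does selecting year-1 responders into the extension bias its 0–36 month height SDS outcome?

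*Combined protocol and SAP*

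**What the plan says.** Under Background and Preliminary Results, Section 6 says that patients with a "year-1 increase in height SDS $> + 0.3$ will qualify to enroll in the extension trial". Under Study Recruitment it repeats the restriction: "Only study participants that have had a satisfactory response to GH within the first year of treatment will have the opportunity to enroll". Its definition of a satisfactory response reads: "This is defined as an increase of height SDS of + 0.3 or greater". The extension's primary objective is to "Describe the continued effects (beyond year 1) of GH therapy on growth parameters in pre-pubertal children with ACAN deficiency". Its primary outcome has two parts: "Change in height SDS from 12 to 36 months, and overall delta height SDS from start of therapy to 36 months".

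The condition also appears outside Section 6. The primary objective in Section 4 makes the further two years depend on the first-year objectives being met. Subject Recruitment/Consent in Section 5 limits the extra consent to those who meet the continuation criteria.

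On how many went on, Section 5 says that "all 10 subjects are past the one-year treatment mark" and that near-complete compliance and "persistence with the protocol has been observed in our cohort so far for patients at least one year on therapy". The Study protocol part of Section 6 says "All patients currently in the treatment trial will continue to receive once daily injections". None of these is a count of children who met the threshold.

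Section 11 (Statistical Considerations) describes all outcome measures as descriptive and plans no formal comparison.

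**The concern.** The 0–36 month change equals the year-1 gain plus the 12–36 month change. Entry depends on the year-1 gain, so this part of the primary outcome contains the variable that decides who contributes to it. If a child with a small year-1 gain is left out, the mean over the rest is expected to exceed the mean over all 10, unless later growth reverses the difference.

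The extension objective speaks of children with ACAN deficiency without adding that they responded in year 1. A mean counted from the start of therapy invites the reading that any child who begins GH can expect that gain. Section 11 does not mention the extension or its analysis set. The interim evidence that everyone would qualify is a projection from five children: the lowest annualised gain of +0.5 is about 0.5 × 0.5 year = +0.25 as measured at 6 months. At stake is how a small, much-read result in a rare disorder would be interpreted.

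**Working it through.** **Inputs.** Planning mean 0.407, SD 0.343 and n = 10 (Section 11). Threshold +0.3, and five interim children with annualised mean gain 0.8, range 0.5 to 1.4 (Section 6). The SD for the remaining five children is not given and is assumed to lie between 0.25 and 0.45. The interim range suggests about (1.4 − 0.5)/2.326 = 0.39, where 2.326 is the expected range of five normal values in SD units.

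**The plan's own figure.** The stated 90% power for the 12-month outcome reproduces. The noncentrality is 0.407/0.343 × √10 = 3.75, and a two-sided one-sample t-test at an assumed alpha of 0.05 has power 91.5%. That outcome covers children whatever their response, so the entry rule does not touch it.

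**Identity.** With k non-qualifiers among 10, the overstatement in the year-1 part is

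mean(qualifiers) − mean(all 10) = (k/10) × [mean(qualifiers) − mean(non-qualifiers)].

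For k = 0 this is exactly zero.

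**Size if someone missed.** Hold the five interim children at their mean of 0.8 as qualifiers and draw the other five with mean 0.8 and SD s. Two shapes were used: normal, and log-normal with the same mean and SD, which suits the right-skewed interim range better. The chance p that one child qualifies is 1 − Φ((0.3 − 0.8)/s) for the normal. At s = 0.343 that is 1 − Φ(−1.458) = 0.928, so all five qualify with probability 0.928⁵ = 0.69. Results from 400,000 simulated trials per setting:

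| s | Normal: p | all 10 qualify | average overstatement | Log-normal: p | all 10 qualify | average overstatement |
|---|---|---|---|---|---|---|
| 0.25 | 0.977 | 89% | +0.007 | 0.999 | 99% | +0.000 |
| 0.343 | 0.928 | 69% | +0.024 | 0.985 | 93% | +0.004 |
| 0.39 | 0.900 | 59% | +0.036 | 0.971 | 86% | +0.008 |
| 0.45 | 0.867 | 49% | +0.051 | 0.946 | 76% | +0.015 |

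Given exactly one non-qualifier, the overstatement is +0.06 to +0.08 (normal) or +0.05 to +0.06 (log-normal). At s = 0.343 under the normal, for example, it is (1/10) × (0.82 − 0.15) = +0.067. Two non-qualifiers under the normal give +0.12 to +0.15.

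**Upper illustration.** With the retrospective planning values, p = 1 − Φ((0.3 − 0.407)/0.343) = 0.622 and the mean gain among qualifiers is 0.616, so the overstatement is 0.616 − 0.407 = +0.21. The interim data do not support these values: five of five gains at or above +0.5 would have probability 0.393⁵ = 0.009.

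**Scope.** These figures cover only the year-1 part. The 12–36 month part does not contain the year-1 gain. It does share the month-12 height with the entry rule, so a chance high reading at month 12 pushes it down rather than up, and that error cancels in the 0–36 month change.

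**The case for a change.** The strongest case for acting is that a sentence would cost almost nothing. All 10 children have passed month 12, so the number who met the threshold can be known from scheduled heights, and the documents do not give it. The sentence that all current patients continue follows directly after a responders-only rule and carries no count. Persistence describes adherence and retention, not response. With 10 children, one or two non-qualifiers would shift the mean by an amount that is visible against a threshold of 0.3.

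All of that is true, and the missing count stands as a gap in the text. It does not make the plan unsound. The outcome sits under the extension heading, between two statements of the responder rule, so its natural reading is extension participants. For them the result is correct as described. Any report of the extension will give the number analysed. A reader can also recover the year-1 part by subtracting the 12–36 month mean from the 0–36 month mean in the same children, and compare it with the 12-month result. No test or error rate is involved. No passage shows a non-qualifier.

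Two further points add little. The threshold is worded as strictly greater in one place and as equal or greater in another, which matters only for a gain of exactly +0.3. The advice to seek local care after stopping GH (Section 6) and the request to complete assessments to the 3-year visit (Section 9) can both be followed, so they do not conflict over who has a 36-month height.

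**Conclusion.** The structural observation is right: the 0–36 month outcome includes the gain that governs entry, and the count of qualifiers is not stated. It is a reporting detail that analysts fill sensibly, not a fault in the analysis. The overstatement is zero if all 10 entered. On the assumptions above its year-1 part is about +0.05 to +0.08 SDS if one child missed, and on average no more than about +0.05 (normal) or +0.02 (log-normal), against an interim mean gain of 0.8. This rests on the interim mean holding for the other five children, on annualised 6-month gains lasting to month 12, and on the assumed SDs. If fewer than 10 entered, a careful report would say so and describe the 0–36 month mean as that of year-1 responders. The two threshold wordings are a clerical inconsistency, to be reconciled as text when the document is next edited, with no effect on the analysis.

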11. STATISTICAL CONSIDERATIONS

This is a pilot single arm study and thus no formal statistical comparison is planned. The outcome measures will all be descriptive. Therefore, we based our power calculations on our ability to confidently detect a positive effect on height SDS. We based the power calculation on our retrospective data. This sample size calculation is based on the following key assumptions: the mean first year response to GH of the 13 previously treated patients in our retrospective data was 0.407 SDS with a standard deviation of 0.343 SDS. We estimated that a sample size of 10 subjects will give us 90% power to demonstrate a change in SDS greater than zero at one-year post treatment initiation. Based on the retrospective data, we are 95% confident that the true mean response falls within the confidence interval of 0.19 to 0.62 SD. This sample size is feasible given the available patient population and estimated budget.

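### Sections 6 and 9 disagree on follow-up after growth hormone stops, and no rule says which children the 36-month outcome covers, so it may over-represent those who kept responding

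*Combined protocol and SAP*

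**What the plan says.** **Stop reasons.** Section 6, under "Reasons for Completion of the Clinical Trial Participation", gives four reasons for ending GH in the extension. Three concern growth or maturation: "The participant reaches skeletal maturity according to their most recent bone age x-ray"; "The participant has a height velocity of <2.5 cm/yr"; and "The participant and/or his/her family feels continued therapy does not lead to satisfactory treatment response". The fourth is the end of the trial or its funding. The same subsection directs children who leave treatment to a local endocrinologist and names no further study visit for them.

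**Primary outcome.** Section 6, Endpoints, sets "Change in height SDS from 12 to 36 months, and overall delta height SDS from start of therapy to 36 months". Both changes need a height at month 36. Heights are also scheduled at 18, 24 and 30 months, but this outcome does not use them.

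**Follow-up elsewhere.** Section 9 (Adverse Events) says that subjects who require GH discontinuation will be asked to complete all assessments up to the 3-year visit.

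**Analysis.** Section 11 says "This is a pilot single arm study and thus no formal statistical comparison is planned" and that all outcomes are descriptive. It does not define the children summarised in the extension, the handling of a missing month-36 height, or the use of heights taken after GH stops. Section 5 adds "Any future drop out from the study will not be replaced by new recruitment".

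**The concern.** Stopping GH depends on the response being measured. If a child who stops also leaves the study, that child has no month-36 height and falls out of both primary changes. The children who remain would then tend to be those still growing well, and the mean gain would be too high. The error would favour the extension's hypothesis of continuing catch-up growth. Children who mature early are of particular interest in this disease and may be among those lost.

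There is a second gap even if every child returns. A child who stopped at month 24 and is measured at month 36 contributes one year on GH and one year off it. The extension's objective is the continued effect of GH. The plan does not say whether the 36-month figure means the outcome whatever happened to treatment, or the change while on treatment.

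**Working it through.** **1. The plan's own figure.** The only power statement (Section 11) concerns year 1: mean 0.407 SDS, SD 0.343, n = 10, 90% power. A one-sample t-test has noncentrality 0.407/0.343 × √10 = 3.75 on 9 degrees of freedom. At two-sided 0.05 (assumed, since the plan gives no level) power is 91.5%, so the figure reproduces. It says nothing about month 36, for which the plan gives no calculation.

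**2. The two follow-up texts side by side.**

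| | Section 6 | Section 9 |
|---|---|---|
| Setting | Extension stop reasons | Adverse events |
| Effect of stopping GH | Treated as completing participation | Assessments still requested to year 3 |
| Later visits | Local care; none named in the study | All, including month 36 |

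Section 9 could be read as covering every discontinuation or only those prompted by an adverse event. The text does not settle this.

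**3. Excess if stopped children have no month-36 height.** Let n children enter and k be missing, with mean gains C in completers and S in stoppers, and D = C − S. The all-entrant mean is [(n − k)C + kS]/n, so completers exceed it by (k/n) × D.

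D is not in the documents. As a guide, assume normal growth of 5 to 6 cm/yr and a height SD of 5 to 6.5 cm. A child growing at 2.5 cm/yr then changes by (2.5 − 5)/6.5 = −0.38 to (2.5 − 6)/5 = −0.70 SDS per year. I take D from 0.3 to 1.0 SDS. With n = 10:

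| k missing | D = 0.3 | D = 0.5 | D = 1.0 |
|---|---|---|---|
| 1 | 0.03 | 0.05 | 0.10 |
| 2 | 0.06 | 0.10 | 0.20 |
| 3 | 0.09 | 0.15 | 0.30 |

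If only eight enter, k = 1 or 2 gives 0.3/8 = 0.04 up to 2 × 1.0/8 = 0.25.

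**4. Cross-check.** Suppose the lowest responders of ten are always the ones missing. With SD 0.343 the excess is 0.06 for one child and 0.11 for two; with an assumed SD of 0.5 it is 0.09 and 0.16.

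**5. Simulation (all settings assumed).** Eight entrants; true mean 12-to-36-month change +0.1 to +0.4 SDS; slope SD 0.15 to 0.30 SDS/yr; height error 0.06 SDS. The velocity rule acts together with a 30% chance of leaving at each of months 24 and 30 if SDS has fallen. Between 0.5 and 2.0 children stop. The completers' excess runs from 0.431 − 0.400 = 0.03 to 0.300 − 0.106 = 0.19. The velocity rule alone gives 0.00 to 0.06.

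**6. Would a random-slope model on the on-GH heights repair it?** With straight-line growth and stopping driven by recorded heights, yes: 0.193 against a true 0.195. With 15% of children stopping for maturity at month 24 and then losing an extra 0.7 SDS/yr, the truth is 0.088, the model gives 0.196 and completers 0.303. The model removes (0.303 − 0.196)/(0.303 − 0.088) = 50% of the excess. If response also wanes, the figures are 0.084, 0.248 and 0.263, and it removes (0.263 − 0.248)/(0.263 − 0.084) = 8%. Convergence warnings were frequent with eight children.

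**7. If Section 9 applies to every stop and is followed,** k = 0 and the excess from missing heights is 0.

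**The case against.** The strongest reply is Section 9. Stopping GH is not the same as losing the month-36 height, and a plan that asks for every assessment to year 3 has no missing-height bias if the request is met. This stands as far as Section 9 reaches. But it sits in the adverse-event section, while the extension's own rules treat the same children as having completed participation. It also leaves open how on-GH and off-GH time are to be reported.

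The second reply is that few children may stop. Section 5 reports near-complete adherence and persistence, in some children to 30 months. The lowest annualised velocity among the five children in Section 6 is 7.4 cm/yr, about three times the 2.5 cm/yr threshold. This lowers the likelihood of a large effect. However, those velocities are six-month results, and the disease is marked by premature growth cessation.

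Third, interim heights do enter the secondary outcomes through yearly height velocity, so slowing before a stop could be seen there. That is correct, but it does not repair the primary figure.

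A reader might infer that the 36-month gain will come mainly from responders, or that early-maturing children are bound to be lost. The documents support neither. They give no number of stops, and Section 9 may keep these children in follow-up.

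**Conclusion.** The point holds as a conditional one. Stopping depends on response, the primary outcome needs a month-36 height, the two sections point different ways on whether that height will be sought, and no analysis rule covers the gap. If Section 6 governs, the 12-to-36 and 0-to-36 month gains may be biased upward. The illustrative size is 0.03 to 0.20 SDS with one or two of ten children missing. For scale, that is 0.03/0.407 = 7% to 0.20/0.407 = 49% of the year-1 effect assumed in Section 11. If Section 9 governs and is followed, the bias from missing heights is nil.

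The range rests on the assumed number missing and the assumed difference D. It is not an estimate for this trial. The quoted velocity rule alone accounts for little (0.00 to 0.06 SDS in the simulation); the larger values need further response-related departures, for which the documents give no rate.

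The year-1 gain of about +0.3 SDS required for entry is a separate selection. It affects the 0-to-36 month figure whatever is decided here.

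**What to change.** 1. Reconcile Sections 6 and 9 so that the already scheduled month-36 height is sought from every child who enters the extension, whatever the reason GH stopped.
2. In Section 11, define the primary summary of both changes on all extension entrants, not on completers, and state how a missing month-36 height is handled.
3. Report separately the change while on GH, using the scheduled 18-, 24- and 30-month heights up to stopping.
4. List for each stopped child the stop month, the reason and the last on-GH change in height SDS. With at most ten children this is easy and informative.
5. A random-slope model on all on-GH heights may be added as a sensitivity analysis. Say that it does not fully correct for growth lost after skeletal maturity and may be unstable at this sample size.

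The cost is one paragraph in Section 11, an aligned sentence in Sections 6 and 9, and possibly a less favourable 36-month figure. The heights are already in the schedule; the added effort is seeing children who have stopped GH at month 36. No change to the clinical stop rules is proposed.
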